16.3 Analysis Plan

The analysis for this trial will commence at planned time points (see 16.2) and at the time the patients have become evaluable for the primary endpoint. The Statistician and Study Chair will make the decision, in accord with CCS Standard Operating Procedures, availability of data for secondary endpoints (e.g., laboratory correlates), and the level of data maturity. It is anticipated that the earliest date in which the results will be made available via manuscript, abstract, or presentation format is when last patient has been followed for at least 6 months.

16.31 Primary Outcome Analyses:

16.311 **Definition:** The primary endpoint of this trial is the proportion of the confirmed response rate. A success is defined as an sCR, CR, VGPR, or PR noted as the objective status on two consecutive evaluations. All patients meeting the eligibility criteria who have signed a consent form and have begun treatment will be evaluable for response, unless they are determined to be a major violation.

16.312 **Estimation:** The proportion of successes will be estimated by the number of successes divided by the total number of evaluable patients. Ninety-

five percent confidence intervals for the true success proportion will be calculated according to the approach of Duffy and Santner.

- 16.313 Over Accrual: If more than the target number of patients are accrued, the additional patients will not be used to evaluate the stopping rule or used in any decision making processes; however, they will be included in final point estimates and confidence intervals.

16.32 Secondary Outcome Analyses

- 16.321 Type of response will be differentiated as biochemical vs. extramedullary disease, as defined in Section 11.6. Biochemical response will be defined as a response by serum M-protein, urine M-protein, or serum FLC assay parameters. For biochemical response, the response rate will be estimated by the number of responders divided by the number of evaluable patients who have measurable disease by serum M-protein, urine M-protein, or serum FLC assay at baseline. Extramedullary response will be defined as a response by extramedullary plasmacytoma or plasma cell count parameters. For extramedullary response, the response rate will be estimated by the number of responders divided by the number of evaluable patients. Exact binomial confidence intervals will be calculated.
- 16.322 Progression-free survival is defined as the time from registration to the earliest date of documentation of disease progression or death due to any cause. The distribution of progression-free survival will be estimated using the method of Kaplan-Meier.
- 16.323 Adverse Events: All eligible patients that have initiated treatment will be considered evaluable for assessing adverse event rate(s). The maximum grade for each type of adverse event will be recorded for each patient, and frequency tables will be reviewed to determine patterns. Additionally, the relationship of the adverse event(s) to the study treatment will be taken into consideration.

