2.2 Secondary

2.21 To determine the toxicities associated with ixazomib in combination with pomalidomide and dexamethasone in patients with previously treated MM with extramedullary disease.

2.22 To determine the differential response rates (biochemical versus extramedullary disease) with ixazomib in combination with pomalidomide and dexamethasone in patients with previously treated MM with extramedullary disease.

2.23 To determine the progression free survival following treatment with ixazomib in combination with pomalidomide and dexamethasone in patients with previously treated MM with extramedullary disease.

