3.2 Registration - Exclusion Criteria

- 3.21 Other malignancy requiring active therapy.
EXCEPTIONS: Non-melanoma skin cancer, DCIS or carcinoma-in-situ of the cervix.
NOTE: If there is a history or prior malignancy, they must not be receiving other specific treatment for their cancer.
- 3.22 Any of the following because this study involves an investigational agent whose genotoxic, mutagenic and teratogenic effects on the developing fetus and newborn are unknown:
- Females of childbearing potential (FCBP)[†] must have a negative serum pregnancy test with a sensitivity of at least 50 mIU/mL within 10 – 14 days prior to and again within 24 hours prior to prescribing pomalidomide for Cycle 1 (prescriptions must be filled within 7 days as required by RevAssist), and must either commit to continued abstinence from heterosexual intercourse or begin TWO acceptable methods of birth control, one highly effective method and one additional effective method.
AT THE SAME TIME, at least 28 days before she starts taking pomalidomide FCBP must also agree to ongoing pregnancy testing. Men must agree to use a latex condom during sexual contact with a FCBP even if they have had a successful vasectomy.
See [Appendix IV](#): Pomalidomide Education and Counselling Guidance Document. Patient must follow pregnancy testing requirements as outlined in the POMALYST REMS™ program.
 - Nursing women
 - Men or women of childbearing potential who are unwilling to employ adequate contraception
- 3.23 Other co-morbidity which would interfere with patient's ability to participate in trial, e.g. uncontrolled infection, uncompensated heart or lung disease.
- 3.24 Other concurrent chemotherapy, radiotherapy, or any ancillary therapy considered investigational.
NOTE: Bisphosphonates are considered to be supportive care rather than therapy, and are thus allowed while on protocol treatment.
- 3.25 Patient has \geq Grade 3 peripheral neuropathy, or Grade 2 with pain on clinical examination during the screening period.
- 3.26 Major surgery \leq 14 days before study registration.
- 3.27 Systemic treatment with strong CYP3A4 inducers (e.g. rifampin, rifapentine, rifabutin, carbamazepine, phenytoin, phenobarbital, Gingko biloba, St. John's wort) within 7 days before registration.

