13.6 Ineligible

A patient is deemed *ineligible* if after registration, it is determined that at the time of registration, the patient did not satisfy each and every eligibility criteria for study entry. The patient may continue treatment at the discretion of the physician as long as there are no safety concerns, and the patient was properly registered.

If the patient discontinues treatment, the patient will go to the event-monitoring phase of the study (or off study, if applicable):

- If the patient received treatment, all data up until the point of confirmation of ineligibility must be submitted. Event monitoring will be required per Section 18.0 of the protocol.
- If the patient never received treatment, on-study material and the Off Treatment Form must be submitted. No further data submission is necessary.

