- if 5 or more patients in the first 15 treated patients experience a grade 4 or higher non-hematologic adverse event at least possibly related to treatment.
- if after the first 15 patients have been treated, 30% of all patients experience a grade 4 or higher non-hematologic adverse event at least possibly related to treatment.

We note that we will review grade 4 and 5 adverse events deemed “unrelated” or “unlikely to be related”, to verify their attribution and to monitor the emergence of a previously unrecognized treatment-related adverse event.

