16.6 Results Reporting on ClinicalTrials.gov

At study activation, this study will have been registered within the “ClinicalTrials.gov” website. The Primary and Secondary Endpoints along with other required information for this study will be reported on www.ClinicalTrials.gov. For purposes of timing of the Results Reporting, the initial estimated completion date for the Primary Endpoint of this study is 2.5 years after the study opens to accrual. The definition of “Primary Endpoint Completion Date” (PECD) for this study is at the time the last patient registered has been followed for at least 6 months.

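### The final adverse-event rates (16.323) leave out patients who were dosed and later found ineligible, although the 16.52 stopping rule has no eligibility condition

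*Combined protocol and SAP*

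**What the plan says.** Section 16.323 defines the set for the final toxicity rates: "All eligible patients that have initiated treatment will be considered evaluable for assessing adverse event rate(s". The worst grade of each event type per patient is then tabulated in that set. This is the analysis of secondary goal 2.21: "To determine the toxicities associated with ixazomib in combination with pomalidomide and dexamethasone in patients with previously treated MM with extramedullary disease".

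Section 13.6 makes ineligibility a finding that comes after registration. It applies when "it is determined that at the time of registration, the patient did not satisfy each and every eligibility criteria for study entry". Such a patient need not stop: "The patient may continue treatment at the discretion of the physician as long as there are no safety concerns", provided registration was proper. For those who do stop, "If the patient received treatment, all data up until the point of confirmation of ineligibility must be submitted", followed by event monitoring. Patients who never receive treatment form a separate category, cancels (13.8).

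The other safety provisions use different sets. The first limb of the stopping rule in 16.52 acts "if 5 or more patients in the first 15 treated patients experience a grade 4 or higher non-hematologic adverse event". Its second limb applies a 30% threshold to all patients once 15 have been treated. The early safety look in 16.4 uses the first 6 patients accrued. Routine event submission (10.62) applies to any patient. None of these mentions eligibility.

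On publication, 16.6 states: "The Primary and Secondary Endpoints along with other required information for this study will be reported on" the public registry.

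**The concern.** A toxicity rate should describe everyone exposed to the drugs. Restricting to eligible patients can be defended for a response rate, where the question concerns a defined population. It is hard to defend for safety, because an event in a dosed patient is evidence about the regimen whether or not an entry criterion was missed.

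The omission also need not be random. Several entry criteria screen for the toxicities that 10.6 grades at each evaluation: neutrophil and platelet counts (3.13), diarrhea (3.29g) and peripheral neuropathy (3.25, which excludes patients at or above "Grade 3 peripheral neuropathy, or Grade 2 with pain on clinical examination during the screening period"). A patient who slipped past one of these may be more likely to show that very event. This is plausible, but nothing in the documents shows it.

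At stake is the published toxicity profile of a new three-drug combination in about 30 patients. Event counts can only fall under the restriction, and rates can move either way. An event that helped to suspend accrual under 16.52 could be absent from the final table.

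**Working it through.** **What the eligibility condition does.** The 16.323 set is patients who are eligible and have started treatment. Cancels fail the second condition already. The first condition therefore removes only patients who were dosed and later ruled ineligible. Nothing elsewhere in the documents puts them back into the final tables.

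**The plan's own design figures.** These do not test the point, but they show what the fix leaves alone. With stopping at 2 or fewer successes in 10 and success at 10 or more in 27, the probability of declaring the regimen promising is the sum over x = 3 to 10 of P(X₁ = x) × P(X₂ ≥ max(0, 10 − x)), where X₁ ~ Bin(10, p) and X₂ ~ Bin(17, p). This gives 0.0994 at p = 0.25 and 0.9036 at p = 0.50, against 0.10 and 0.90 in 16.24. The interim stopping probabilities are 0.5256 and 0.0547, against 0.53 and 0.05. The table reproduces.

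**Inputs for the size.** Section 16.22 plans 27 evaluable patients plus 3 for ineligibility, cancellation, major violation and other reasons, 30 in total. The number of dosed ineligible patients, k, is not given. I assume 30 dosed and k = 1 or 3. Three is a ceiling, because the same allowance covers the other causes.

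**Example 1: 6 eligible patients have the event.** Reported rate = 6/(30 − k). The all-dosed rate runs from 6/30 (no excluded patient had it) to (6 + k)/30 (all did).

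| k | Reported under 16.323 | All dosed |
|---|---|---|
| 1 | 6/29 = 20.7% | 6/30 = 20.0% or 7/30 = 23.3% |
| 3 | 6/27 = 22.2% | 6/30 = 20.0% to 9/30 = 30.0% |

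**Example 2: 9 of 30 dosed have the event (30.0%, the second 16.52 threshold).** Reported rate = (9 − j)/(30 − k), where j is the number of excluded patients with the event.

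- k = 1: 8/29 = 27.6% or 9/29 = 31.0%.
- k = 3: from 6/27 = 22.2% to 9/27 = 33.3%.

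**Example 3: the first 16.52 limb.** 5/15 = 33.3% suspends accrual. If one of those five is later found ineligible, the 16.323 rate in the same cohort is 4/14 = 28.6%.

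**Example 4: an event in one of 30 dosed patients.** If exclusion is unrelated to the event, the chance that the table shows zero is k/30: 1/30 = 3.3% to 3/30 = 10.0%.

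**Response rate, a minor side point.** Section 16.311 also excludes ineligible patients, and major violations as well. With 30 treated and 10 responders among evaluable patients, one exclusion gives 10/29 = 34.5% against 10/30 = 33.3% or 11/30 = 36.7%. Three give 10/27 = 37.0% against 33.3% to 13/30 = 43.3%. This does not show the stated 0.10 error rate to be wrong for the evaluable set.

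**The case against.** The strongest reply is that very few patients will be affected, perhaps none. Section 6.2 has eligibility verified before a registration is accepted, and 6.12 requires a completed checklist from outside sites. Three dosed ineligible patients would need the whole allowance to go to one cause. With one such patient, Example 1 shifts by 0.7 or 2.6 percentage points, while the exact 95% interval for 6/30 runs from 7.7% to 38.6%. All of this stands. It limits the size of the problem, but gives no reason to drop exposed patients.

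The comparison with 16.52 can also be pressed too far. Only its first limb refers to treated patients; the second says all patients. The rule covers grade 4 or higher, non-hematologic events at least possibly related to treatment, whereas 16.323 tabulates every event type. The 9/30 case arises only when planned accrual is complete, so it changes no accrual decision. These points are fair. The two sections serve different purposes, and the numerical contrast holds only for the same event definition. Neither limb has an eligibility condition, however, so the difference in populations remains.

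Finally, the direction of bias is unknown, the events are still collected and seen in monitoring, and 16.6 promises further required information whose content is not stated. It therefore cannot be established that these events would be missing from the public record altogether. What can be said is that the planned rates would not contain them.

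**Conclusion.** The concern holds. As written, 16.323 removes dosed patients from the reported toxicity rates and no other provision restores them. Monitoring, expedited reporting and the response decision rules are not affected.

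The size depends on an unstated number. With one dosed ineligible patient among 30, rates near 20% to 30% move by roughly 1 to 3 percentage points. At the ceiling of three, a 30.0% rate could appear as low as 22.2% or as high as 33.3%. The more practical loss is a single-patient event dropping out of the table. The 3.3% to 10.0% chance assumes that 1 to 3 such patients exist and that exclusion is unrelated to the event; the unconditional chance is lower and unknown. The wording problem is certain and its consequence is probably small. It should be corrected because the correction is nearly free.

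**What to change.** Replace the population sentence in 16.323 with: *Every patient who takes at least one dose of any study drug is included in the adverse-event analysis, whether or not later found ineligible.* An eligible-only table can be kept as support. State in both limbs of 16.52 that the same set applies.

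Clarify 13.6 as well. For a treated ineligible patient who stops, data are required only up to confirmation of ineligibility, plus event monitoring, so later adverse events may have to be requested. Most other data are already collected under 10.62.

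Optional and minor: keep the interim rule and the 10/27 rule on the evaluable set, and add to 16.31 a sensitivity estimate of response in all treated patients. Count excluded patients as non-responders unless a confirmed response is documented, and list the number of exclusions and the reason for each. This matters mainly for major violations, because the judgement in 13.7 has no deadline and is not separated from knowledge of response.

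The cost is one line of text, a little more analysis, and possibly slightly less favourable reported rates. Design, sample size and error rates do not change.

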6.8 Baseline symptoms

All required baseline symptoms (see Section 10.62) must be documented and graded.

6.9 Study drug is available on site.

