10.6 Required routine reporting

Adverse events to be graded at each evaluation and pretreatment symptoms/conditions to be evaluated at baseline per the CTCAE v4.0 grading unless otherwise stated in the table below:

SYSTEM ORGAN CLASS	Adverse event/Symptoms	Baseline	Each evaluation
Investigations	Creatinine increased	X	X
	Neutrophil count decreased	X	X
	Platelet count decreased	X	X
General disorders and administration site conditions	Fatigue	X	X
Gastrointestinal Disorders	Nausea	X	X
	Vomiting	X	X
	# of Stools	X	
	Diarrhea		X
	Constipation		X
Infections and infestations	Sepsis	X	X
Blood and lymphatic system disorders	Febrile neutropenia	X	X
Skin and subcutaneous tissue disorders	Rash, maculopapular	X	X
Nervous system disorders	Peripheral sensory neuropathy	X	X
	Peripheral motor neuropathy	X	X

10.62 Submit via appropriate MCCC Case Report Forms (i.e., paper or electronic, as applicable) the following AEs experienced by a patient and not specified in Section 10.5:

10.621 Grade 2 AEs deemed *possibly, probably, or definitely* related to the study treatment or procedure.

10.622 Grade 3 and 4 AEs regardless of attribution to the study treatment or procedure.

10.623 Grade 5 AEs (Deaths)

- Any death within 30 days of the patient's last study treatment or procedure regardless of attribution to the study treatment or procedure.
- Any death more than 30 days after the patient's last study treatment or procedure that is felt to be at least possibly treatment related must also be submitted as a Grade 5 AE, with a CTCAE type and attribution assigned.

10.63 Refer to the instructions in the Forms Packet (or electronic data entry screens, as applicable) regarding the submission of late occurring AEs following completion of the Active Monitoring Phase (i.e., compliance with Test Schedule in Section 4.0).

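### The adverse-event tables use each patient's maximum grade with no role for the baseline grade, so unchanged low-grade neuropathy or low counts present at entry can be counted on study

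*Combined protocol and SAP*

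**What the plan says.** Section 16.323 defines the adverse-event analysis for eligible patients who started treatment: "The maximum grade for each type of adverse event will be recorded for each patient, and frequency tables will be reviewed to determine patterns". It adds: "Additionally, the relationship of the adverse event(s) to the study treatment will be taken into consideration". It has no new-or-worsened rule, no shift table and no definition of a treatment-emergent event.

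The baseline data largely exist. Section 10.6 opens: "Adverse events to be graded at each evaluation and pretreatment symptoms/conditions to be evaluated at baseline per the CTCAE v4.0 grading". Its table marks creatinine, neutrophils, platelets, fatigue, nausea, vomiting, maculopapular rash, and sensory and motor neuropathy (with sepsis and febrile neutropenia) for both baseline and each evaluation. No attribution condition is attached. Section 6.8 makes the baseline step compulsory: "All required baseline symptoms (see Section 10.62) must be documented and graded". (It points to 10.62, but the table stands in 10.6.)

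The population is previously treated (3.12). For neuropathy, Section 3.25 excludes only patients at or above "Grade 3 peripheral neuropathy, or Grade 2 with pain on clinical examination during the screening period". Section 3.13 admits platelets from 50,000/mm3, ANC from 1000/mm3, hemoglobin from 8.0 g/dL and creatinine clearance from 30 mL/min.

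**The concern.** Secondary objective 2.21 is to describe the toxicities associated with the regimen. A per-patient maximum that ignores the starting grade cannot separate a new event from one the patient brought in. In a previously treated population, both residual neuropathy and low counts at entry are permitted.

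The problem sits in the low grades and in the solicited items. Terms outside the solicited list pass a filter: under 10.621 a Grade 2 event is submitted only if judged at least possibly related. Items in the 10.6 table pass no such filter and are graded at each evaluation regardless.

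Comparability also suffers. The reference rates that a reader would set beside this trial's results, in Tables 1-2 and 1-3, are labelled treatment-emergent. A table that may include unchanged entry conditions is not on the same footing.

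**Working it through.** Section 16.323 states no figure to reproduce, so the check is a reading of the rules followed by an illustration.

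**One patient followed through the rules**
- Entry: painless Grade 2 sensory neuropathy, admissible under 3.25.
- Baseline: recorded as Grade 2 (6.8, 10.6).
- Each evaluation: graded again, still 2 (10.6).
- Analysis: maximum grade = 2, so the patient appears as Grade 2 neuropathy (16.323 read literally).
- Under a new-or-worse rule: 2 is not above 2, so the patient is not counted.

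**Which grades are exposed**
- Neuropathy: Grade 3 or higher is excluded at entry, so only Grades 1 and 2 can be carried in.
- Platelets: Table 8.3 puts Grade 3 below 50,000/mm3, and entry requires at least 50,000/mm3, so again only lower grades.
- ANC: the documents do not give the grade cut-offs, so I have not mapped the 1000/mm3 limit to a grade.

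**Which decisions are exposed**
- The DLT definition (16.4) requires at least possible attribution and an event occurring in cycle 1.
- The stopping rule (16.52) counts only non-hematologic events of Grade 4 or higher with at least possible attribution.
- Neither turns on unchanged low-grade entry conditions. Sample size, alpha and power rest on response, not on these tables.

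**Illustration for any-grade neuropathy**

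Inputs:
- r, the new-event rate: 26% (45 of 173, Table 1-3, oral combinations) or 10% (21 of 201, Table 1-2, single agent).
- b, the share entering with Grade 1 or 2 neuropathy: not in the documents. I assume 20%, 30% and 50%.

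If every entry neuropathy persists, no attribution filter is applied, and r is the same whatever the baseline status:

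tabulated rate = b + (1 − b) × r, and excess over r = b × (1 − r)

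| b | r = 26%: tabulated | excess | r = 10%: tabulated | excess |
|---|---|---|---|---|
| 20% | 0.20 + 0.80 × 0.26 = 40.8% | 14.8 points | 0.20 + 0.80 × 0.10 = 28% | 18 points |
| 30% | 0.30 + 0.70 × 0.26 = 48.2% | 22.2 points | 0.30 + 0.70 × 0.10 = 37% | 27 points |
| 50% | 0.50 + 0.50 × 0.26 = 63.0% | 37.0 points | 0.50 + 0.50 × 0.10 = 55% | 45 points |

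Taking 27 patients and r = 26%, that is about 11, 13 or 17 patients tabulated, against 7 with a new event. All of the excess is Grade 1 or 2.

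**How far r = 26% transfers.** Table 1-3 pools C16005, C16006, C16008 and C16013. Table 1-1 lists the first three as newly diagnosed (65 + 20 + 64 = 149) and only C16013 (9) as relapsed or refractory. These sum to 158 rather than 173, so the exact mix is uncertain, but the pool is plainly mostly newly diagnosed.

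**The case against.** The strongest reply is that the plan is silent, not wrong. A reader might infer that it counts entry conditions as toxicities of the regimen. The documents do not say that: 16.323 has relationship to treatment considered in the same paragraph, and 10.6 names pretreatment conditions separately from adverse events. The manufacturer-reporting instructions in 10.43 treat a clinically relevant worsening as an adverse event, which suggests that an unchanged finding is not one. Sections 8.11 and 8.2 use baseline severity as a working concept. For neuropathy that never changes, an investigator can simply choose one of the two lowest attribution categories in 10.3.

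Much of this stands, and it is why the point is that such conditions can be counted, not that they are. It does not close the gap. The 10.43 wording governs reporting to the manufacturer, and the Section 8 wording governs dose management; neither is an analysis rule. Taking relationship into consideration does not restrict any table to related events. Attribution is also a weak substitute for baseline here: peripheral neuropathy is listed as very common for both ixazomib (15.17) and pomalidomide (15.27), so a persisting case could readily be coded as possible.

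It is also fair that the illustrated rates rest on an assumed prevalence and sit at the upper end, and that this is a descriptive analysis in a single-arm trial of about 30 patients with no test on adverse events.

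Finally, baseline grades are not available for every item. In 10.6, constipation has no baseline entry, diarrhea has a baseline stool count instead of a grade, and anemia is not listed.

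**Conclusion.** The concern holds as a gap in the analysis rule. Followed literally, 16.323 lets unchanged low-grade conditions present at entry appear in the all-attribution tables, which can overstate the regimen's toxicity under objective 2.21.

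The size cannot be determined from the documents. It could be nil if stable conditions were all judged unrelated and only related events were tabulated. At the upper end, with a 26% new-event rate and 20% to 50% prevalence at entry, any-grade neuropathy would read 41% to 63%. That rests on persistence of entry neuropathy, no attribution filter, an equal new-event rate whatever the baseline, and a rate borrowed from mostly newly diagnosed patients. I put no figure on the cytopenias.

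A reader might go further and infer that severe-toxicity rates or the safety rules are distorted. The documents do not support that: the entry limits keep neuropathy and platelets below Grade 3 at baseline, and the DLT and stopping rules require attribution. This is an inexpensive correction to a descriptive secondary analysis, worth making before tables are produced.

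**What to change.** In 16.323:
- Tabulate the maximum post-baseline grade only for events that are new or worse than the patient's own baseline grade.
- For the solicited items graded at baseline under 10.6, add a table of baseline grade by maximum post-baseline grade.
- Present the tables twice: regardless of attribution, and for events judged at least possibly related.
- For items without a baseline grade, state the convention: derive anemia from the baseline CBC, use the baseline stool count for diarrhea where possible, and report constipation unadjusted with a note.

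The cost is a sentence or two in the plan and a little programming. Nearly all the data are already collected, and the design, sample size and safety rules do not change.
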